Potentially eligible subjects will be asked to complete the Informed Consent process, at which point the subjects will read through the IRB-approved consent form, and will meet with a research staff member who will answer any questions, explain the schedule of study procedures, and review the risks and benefits of the study. Subjects will be informed about the experimental nature, purpose, risks, and benefits of the study in accordance with procedures of the Partners IRB. There will be no time-limit placed on the consenting process. Research staff members understand that the consent is a process and not simply a matter of signing and dating the consent form. Either the PI or one of the Co-Investigators (serving as designees of the PI) will be available to help explain the study and answer questions. Once the subject consents to participate in the study, the subject will sign and date the consent form along with a member of the research staff. The subject will be provided with a copy of the consent form and the original will be stored in a secure location by a member of the study staff.

Participants will be randomly assigned to receive either ICBT or IDC. This randomization will be stratified by the following variables: (1) presence of a medication for anxiety, (2) gender, (3) type of opioid medication (agonist/partial agonist vs. antagonist), and (4) severity (defined by presence vs. absence of opioid use since initiating pharmacotherapy for opioid use).

V. STUDY PROCEDURES

All participants will receive 12 individual weekly sessions of ICBT or IDC and will complete assessments at baseline, week 12, and 1- and 3-month post-treatment follow-up visits. Breath alcohol screens will be conducted at each session and assessment visit to confirm absence of acute alcohol use. Procedures for response to a positive breathalyzer screen are specified below in Section VII. Qualitative exit interviews will be conducted at the completion of treatment. These interviews will focus on issues related to feasibility and acceptability, such as identifying the most and least helpful sessions and areas for improvement. Details of the procedures are included below.

V.1. Eligibility and Baseline Assessment

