Female participants will provide saliva samples and will report descriptive data on menstrual cycle phase in order to measure fluctuations in estradiol and progesterone throughout the study period. Salivary assays of estradiol and progesterone will be performed in duplicate and in

accordance with manufacturer specifications at the Laboratory for Biological Health Psychology at Brandeis University. Saliva samples will be collected using the passive drool method and according to recommended collection procedures. Samples will be collected at baseline (immediately prior to the Escape Go/NoGo Task) and at each weekly session. In addition to measurement of salivary estradiol and progesterone, we will also collect descriptive data on menstrual cycle phase (with the Menstrual Cycle Information form), following recommendations for optimizing measurement of menstrual phase (Allen et al., 2016). Specifically, we will utilize both self-reported onset of menses and weekly hormone data to characterize menstrual cycle phase throughout the trial. We will also assess for presence, type, dose, and compliance with birth control at each time point. Furthermore, using the interviewer-administered Saliva Sample Activity Documentation form, we will collect information on participant activity in the past 12 hours that may affect saliva collection.

VI. BIOSTATISTICAL ANALYSIS

Data from this randomized controlled trial will be analyzed using descriptive and qualitative analytic methods as well as traditional significance tests. Measures of patient satisfaction will be considered along with qualitative exit interviews to determine the acceptability of the treatment. Randomized groups will be compared with respect to baseline demographic and clinical variables using t-tests and chi-square tests; if significant group differences are identified in any variables known to be highly predictive of outcome, these variables will be adjusted for via their inclusion as covariates. These covariates will also be summarized with descriptive statistics and graphical methods to determine the most appropriate way to incorporate them in the analyses (e.g., continuous or categorical representation). All outcome analyses will utilize an intent-to-treat approach, complemented by exploratory completer analyses.

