The hypothesis that I-CBT will yield greater reduction in opioid use and anxiety symptoms will be tested using separate linear mixed effects models for opioid use (weeks of use in the previous 4 weeks) and anxiety (HARS score) examining the main effect of treatment condition and its interaction with time on each outcome. The correlation among the repeated measures of the dependent variable will be appropriately accounted for via the inclusion of random subject effects (e.g., random intercepts and slopes for time). Covariates will include pre-treatment values of the dependent variable and any baseline demographic or clinical variables identified as necessary covariates in preliminary analyses.

To test the hypothesis that baseline stress reactivity is associated with treatment outcome at post-treatment (week 12), linear regressions will be utilized with primary opioid and anxiety outcomes at week 12 as the dependent variables and post-stress task anxiety, craving, and heart rate variability as independent variables, co-varying for baseline severity and any other covariates identified in preliminary analyses. In addition, to test the hypothesis that reduction in stress reactivity over time will be greater in the I-CBT condition, a linear mixed effects model will be conducted examining whether stress reactivity decreased from pre- to post-treatment and whether groups differed with respect to this change; this analysis will include the main effects of time and group and the time x group interaction. The correlation among repeated measures of the dependent variable will be accounted for via the inclusion of random subject effects.

With repeated assessments over 7 months of study participation, some amount of missing data is inevitable. Extensive efforts will be made throughout all stages of follow-up to minimize missing data by vigorous outreach, including to any participants who elect to dropout of treatment prior to completion. For all of the proposed analyses, we will use statistical methods (e.g., linear

mixed effects models) that incorporate partially observed data on participants who are lost to follow-up.

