We do not expect more than a 10% loss to follow-up (see C.4); nonetheless, the sample size of 54 participants was selected to provide adequate degrees of freedom to estimate the treatment effect size and its reliability, even when allowing for up to 20% loss to follow-up. In this Stage 1 trial, we will focus on the estimation of effect sizes and clinically-significant change (as defined by Jacobson & Truax, 1991). If promising results (i.e., presence of clinically-significant change) are detected, these data will provide an estimate of the reliability of the effect to inform power calculations for a larger Stage 2 clinical trial. Although the focus of this trial is the estimate of an effect size and its reliability, we have conducted a power analysis for the proposed sample size; effect sizes are expressed as standardized differences in means for ease of interpretation. For Aim 2, based on unpublished data from previous clinical trials, we anticipate a small correlation between repeated measures of the opioid use outcome ($r < .20$) and a small to medium correlation ($r = 0.42$) for the HARS. Thus, the proposed sample size would provide adequate power (power of at least 0.80) to detect a minimum between-group difference from baseline to end of treatment in the magnitude of a large effect size ($d = .70-.75$). For Aim 3, based on previous studies examining stress reactivity and alcohol and cocaine use following treatment, which have consistently reported medium to large effect sizes (Sinha et al., 2009; 2011), the proposed sample size would provide adequate degrees of freedom to detect an effect size in the range of high medium to large.

VII. RISKS AND DISCOMFORTS

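### The Aim 2 models leave out the four stratification factors and, baseline outcome aside, admit covariates only through baseline significance tests; if the factors are prognostic, the test of the treatment main effect is conservative and power is forgone

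*Combined protocol and SAP*

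**What the plan says.** Section IV (Subject Enrollment) sets out a stratified allocation: "This randomization will be stratified by the following variables: (1) presence of a medication for anxiety, (2) gender, (3) type of opioid medication" (agonist or partial agonist against antagonist). The fourth factor is severity, meaning any opioid use since pharmacotherapy began. Block size, list method and allocation ratio are not stated.

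Section VI (Biostatistical Analysis) compares the arms at baseline by t-tests and chi-square tests, and "if significant group differences are identified in any variables known to be highly predictive of outcome, these variables will be adjusted for". Whether such a covariate is treated as continuous or categorical is also left to be settled from data summaries.

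The Aim 2 analysis uses separate linear mixed models for the HARS and for weeks of opioid use, "examining the main effect of treatment condition and its interaction with time on each outcome". On adjustment it says: "Covariates will include pre-treatment values of the dependent variable and any baseline demographic or clinical variables identified as necessary covariates in preliminary analyses". The pre-treatment outcome is therefore always in the model. Nothing else is named, and the stratification factors do not appear anywhere in Section VI.

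The same section gives the purpose of the trial: if results are promising, "these data will provide an estimate of the reliability of the effect to inform power calculations for a larger Stage 2 clinical trial".

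**The concern.** The allocation rule and the covariate rule work against each other. Stratification makes the arms alike on the four factors, while the screen admits only variables on which the arms differ significantly. The variables chosen for control at allocation are thus the ones least likely to reach the model.

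If those factors predict outcome, stratifying on them reduces the true variance of the treatment contrast. A model without them leaves their variation in the residual and reports a standard error that does not credit this reduction. Intervals are too wide, the test rejects too seldom, and the reliability of the effect, which Stage 2 planning is meant to use, is understated.

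A separate matter concerns variables that were not stratified. The screen misses moderate imbalances in prognostic variables, and it leaves the model undetermined until the arms have been compared.

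**Working it through.** **Inputs from Section VI:** N = 54; d = 0.70 to 0.75; correlation between repeated measures 0.42 (HARS) and below 0.20 (opioid use); power at least 0.80; up to 20% loss allowed for.

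**Assumed, not in the documents:** 27 per arm; two-sided alpha 0.05; the four factors explain 0 to 30% of the outcome variance left after baseline; permuted blocks of 2 or 4 within the 2⁴ = 16 strata; factor prevalences 0.50, 0.45, 0.25 and 0.50.

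**1. The plan's own power.** With adjustment for baseline the residual SD is √(1 − r²), and power is Φ(d/√(1 − r²) × √(27/2) − 1.96).
- HARS: √(1 − 0.42²) = 0.908; 0.70/0.908 × 3.674 = 2.83; power 0.81.
- Opioid use, r = 0.20: √(1 − 0.04) = 0.980; 0.75/0.980 × 3.674 = 2.81; power 0.80.

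The stated figure reproduces on the full 54 with baseline as the only covariate. The noncentral t distribution gives 0.79 for both.

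**2. Can the factors pass the screen?** Under simple randomisation at least one of four independent tests is significant with probability 1 − 0.95⁴ = 18.5% (simulated: 18%). Under stratified blocks the simulated figure runs from 0.03% (blocks of 2) to about 1% (blocks of 4). The screened analysis therefore performs like one that omits the factors.

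**3. Standard error, type I error and power for the end-of-treatment HARS difference.** With perfect balance the reported standard error would exceed the true one by the factor 1/√(1 − R²), where R² is the share explained: 1.05, 1.12 and 1.20 at 10, 20 and 30%. With 54/16 = 3.4 participants per stratum many blocks are incomplete, so the simulated excess is smaller. Simulations with r = 0.42, d = 0.70 and no dropout gave the following ranges over separate runs:

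| Share of residual variance explained | 0% | 10% | 20% | 30% |
|---|---|---|---|---|
| Reported/true standard error, factors omitted | about 1.0 | 1.01-1.04 | 1.07-1.09 | 1.10-1.15 |
| Type I error, omitted | about 5% | 4.1-4.5% | 3.3-3.9% | 2.4-3.1% |
| Power, omitted | 78-79% | 79-80% | 79-80% | 81-83% |
| Power, included | 77-78% | about 82% | 85-86% | 90-91% |

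With the factors included, type I error is about 5% throughout. At a 5% share the gain lies between nothing (simulation) and about 2 points (noncentral t, 0.794 to 0.813).

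**4. Treatment by time.** With factor effects constant over time, the reported/true standard error ratio for this term is 0.99 to 1.01 with or without the factors. In a random-intercept mixed model with strong factors, adding them cut the main-effect standard error from 0.207 to 0.167 and left the interaction's at 0.115.

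**5. Variables not used for stratification.** A t-test at 27 per arm flags a difference only above t(0.975, 52) × √(2/27) = 2.007 × 0.272 = 0.546 SD. Suppose one variable is out of balance by 0.4 to 0.5 SD and correlates 0.42 to 0.50 with outcome. The baseline-adjusted estimate shifts by imbalance × (correlation with outcome − correlation with baseline × 0.42).
- Independent of the baseline outcome: 0.4 × 0.42 = 0.17 to 0.5 × 0.50 = 0.25 SD; conditional type I error 7.5 to 12%.
- Correlated 0.3 to 0.5 with it: 0.4 × (0.42 − 0.5 × 0.42) = 0.08 to 0.5 × (0.50 − 0.3 × 0.42) = 0.19 SD; conditional type I error 5.6 to 9.1%.

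Adjusting for the variable restores 5.0%. A given variable falls between 0.4 and 0.546 SD in about 9.8% of trials. These rates are conditional on that event and are not the trial's overall error rate.

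**The case against.** The strongest reply is that no planned property fails. The estimate is unbiased, the test is conservative, and power stays near 0.80, so what is lost is an optional gain whose size is assumed. At a 5% share the gain is close to nil, and for opioid use the severity factor overlaps with baseline use, which makes the upper shares less likely there. All of this stands and limits the weight of the point.

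Dropout also raises the price. At 20% loss, simulated power falls from 68.9% to 66.4% when non-prognostic factors are added, about 2.5 points. If they explain 20%, it rises from 69.0% to 75.8%. The trade-off is real, but still favours inclusion if the factors matter.

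Only one of the two tested terms is affected. The figures above also take the main effect as the week 12 difference, which requires time to be measured from week 12, and the plan does not say so. They come mainly from single-visit regressions; the mixed-model example shows the same pattern.

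Finally, the screen uses baseline data only and also requires a variable known to be highly predictive, and its wording does not formally bar the stratification factors. That is correct. But stratification in practice keeps them out, and the highly predictive variables are not named in advance.

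**Conclusion.** The point holds. The plan stratifies on four factors, does not name them in the Aim 2 models, and relies on a screen they almost cannot pass. The consequence is lost precision on the treatment main effect, not bias or false-positive inflation. It amounts to roughly 2 to 9 points of power over an assumed 10 to 30% explained variance, and to nothing if the factors are not prognostic. It rests on balanced allocation within strata (blocks or minimisation); simple randomisation would not make the test conservative. The treatment-by-time conclusion does not change. The screen has a second weakness that does not depend on the stratification factors: the final covariate set is decided by chance baseline differences. The change is worth making because it is cheap and the trial's declared product is an effect size with its reliability. It does not undermine the trial's validity.

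**What to change.** In Section VI, state that both Aim 2 models include the four stratification factors as main effects together with the baseline value of the outcome. Main effects only: 16 cells are too sparse at N = 54 for a full stratum term. Name in advance, with its coding, any other covariate judged prognostic. Delete the rule that selects covariates by baseline t-tests and chi-square tests, and keep the baseline comparison descriptive.

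The cost is one or two sentences and four residual degrees of freedom, from 54 − 3 = 51 to 54 − 7 = 47 for the end-of-treatment comparison. If the factors are not prognostic, that is about 1 to 1.5 points of power with complete data, and about 1.5 to 2.5 points at the 10 to 20% loss discussed in the plan.

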Specific Aim 2. To examine the efficacy of ICBT for the improvement of opioid dependence and anxiety symptoms relative to Individual Drug Counseling (IDC). We hypothesize that patients will report greater pre-post reductions in interviewer-rated anxiety symptoms and less opioid use in ICBT relative to IDC.

Specific Aim 3. To examine the association between stress reactivity and treatment outcome in opioid-dependent patients. We hypothesize that: (a) higher levels of stress reactivity at baseline will be associated with more days of opioid use following treatment, and (b) reductions in stress reactivity from baseline to post-treatment will be greater in the ICBT group relative to the IDC group.

Specific Aim 4. To examine the association between ovarian sex hormones, negative reinforcement bias, and treatment outcome in opioid-dependent patients. We hypothesize that: (a) greater negative reinforcement bias will be associated with poor treatment outcomes, and that this association will be stronger in women than men, and (b) within women, high progesterone will be associated with lower negative reinforcement bias and less severe opioid symptoms (e.g., opioid craving, anxiety severity).

III. SUBJECT SELECTION

Participants will be recruited for a randomized controlled trial of the efficacy, feasibility, and acceptability of ICBT. We aim to enroll 54 participants in this trial, and anticipate that up to 110 participants will need to complete informed consent and screening in order to initiate treatment. Participants will be recruited via either: (1) invitation to participate by a member of the study staff, or (2) self-selection in response to posted advertisements.

III.1. Inclusion/Exclusion Criteria

Subjects will be **included** if they: (1) are age 18 or older, (2) meet *DSM-5* diagnostic criteria for opioid use disorder, (3) are currently receiving pharmacotherapy for opioid dependence (e.g., buprenorphine, buprenorphine-naloxone, naltrexone, Vivitrol), (4) have used opioids illicitly within the previous 90 days, (5) exhibit clinically-significant anxiety defined as a score of 14 or higher on a clinician-rated anxiety symptom severity scale (the Hamilton Anxiety Rating Scale), (6) meet *DSM-5* diagnostic criteria for a current diagnosis of an anxiety disorder, (7) are able to read and provide informed consent, and (8) intend to remain in the geographical area for the duration of the study period.

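### Hypothesis 3(a) concerns days of opioid use after treatment, but its only planned test uses a week-12 outcome that, for completers, counts weeks of use during treatment

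*Combined protocol and SAP*

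**What the plan says.** Section II, Specific Aim 3, gives a general objective, "To examine the association between stress reactivity and treatment outcome in opioid-dependent patients", and then a specific hypothesis, 3(a): "higher levels of stress reactivity at baseline will be associated with more days of opioid use following treatment". The objective names no unit or time window. The hypothesis names both.

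Section VI restates the hypothesis as whether "baseline stress reactivity is associated with treatment outcome at post-treatment (week 12", closing the bracket there, and gives the method: "linear regressions will be utilized with primary opioid and anxiety outcomes at week 12 as the dependent variables". That sentence does not define the opioid outcome. The only definition in the section is in the preceding paragraph, on Aim 2, where the mixed model is for "opioid use (weeks of use in the previous 4 weeks", again in brackets.

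On timing, section V states "All participants will receive 12 individual weekly sessions of ICBT or IDC", with "assessments at baseline, week 12, and 1- and 3-month post-treatment follow-up visits". Table 1 lists the Timeline Follow-Back among the primary outcomes and schedules it at both follow-up visits. Section VI names no Aim 3(a) analysis that uses those follow-up data, and no analysis of days of use for any aim.

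**The concern.** The hypothesis and its test differ in window and in unit. The hypothesis looks at the time after therapy ends. The test looks back from about the end of therapy, so for most completers it describes use while weekly sessions and weekly urine screens were still going on.

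The two can rank participants in opposite order. Someone abstinent in weeks 9-12 who relapses in the first month afterwards has the best possible score, 0. Someone who used in week 9 and then stayed abstinent scores 1. The coarser unit also hides severity: use on one day in each of four weeks (4 days) and daily use for four weeks (4 x 7 = 28 days) both score 4.

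At stake is what can be concluded. A positive or null week-12 regression could be reported as the answer to 3(a) although it was not designed to observe use after treatment. Leaving two endpoints in the document also leaves room to choose between them after the data are seen.

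**Working it through.** **1. The texts side by side.**

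| | Hypothesis 3(a), section II | Planned test, section VI |
|---|---|---|
| Unit | days of use | weeks with use, 0-4 (carried over from the Aim 2 paragraph) |
| Window | after treatment | 4 weeks up to the week-12 assessment |
| Data source | Timeline Follow-Back at 1 and 3 months would supply it | week-12 visit only |

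**2. How much of the look-back is after treatment.** Treatment occupies weeks 1-12. For a visit at week v with a 4-week look-back, the number of post-treatment weeks is min(4, max(0, v - 12)).

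- Week 12: 0 of 4 (the window is weeks 9-12).
- Visit 1 week after session 12 (assumption): 1 of 4.
- Visit 2 weeks after session 12 (assumption): 2 of 4.
- 1-month follow-up, about week 16: 4 of 4.
- 3-month follow-up, about week 24: 4 of 4.

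The late-visit rows are shown because section IX.1 lists the post-treatment assessment separately from weeks 1-12 and no lag is stated.

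**3. The plan's own design figure.** Section VI gives no number for Aim 3, only a verbal range from upper-medium to large. Its one numeric figure is the Aim 2 detectable difference, d = 0.70-0.75 at power 0.80 with 54 participants. Assuming 27 per arm, two-sided 0.05 and baseline adjustment, d = (1.960 + 0.842) x sqrt(2/27) x sqrt(1 - r^2).

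- r = 0.42 (HARS): 0.692.
- r = 0.20 (upper limit for opioid use): 0.747.

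This matches the stated range, so two-sided 0.05 is a reasonable assumption for the next step. The point itself does not depend on this figure.

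**4. Cost of moving to a follow-up outcome.** For a linear regression testing u predictors out of k, the power is that of a noncentral F with u and N - k - 1 degrees of freedom and noncentrality f^2 x N. Partial r = sqrt(f^2 / (1 + f^2)). Section VI expects at most 10% loss and allows for 20%: 54 x 0.9 = 48.6, taken as 48; 54 x 0.8 = 43.2, taken as 43.

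| N | Partial r, one predictor | Partial r, three reactivity predictors jointly |
|---|---|---|
| 54 | 0.36 (f^2 = 0.151) | 0.42 (f^2 = 0.219) |
| 48 | 0.38 (f^2 = 0.171) | 0.45 (f^2 = 0.249) |
| 43 | 0.40 (f^2 = 0.191) | 0.47 (f^2 = 0.281) |

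The week-12 regression would itself lose some participants, so taking N = 54 as its starting point overstates the cost of the change. A count or proportion of days may need a model other than ordinary least squares, so these values are a guide.

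**The case against.** The strongest reply is that *following treatment* just means at the post-treatment visit, as section VI restates it. On that reading the window is intended, and only the wording of 3(a) is loose. This is a fair reading, but it does not remove the mismatch: the unit still changes from days to weeks, and a four-week look-back from the end of treatment still mostly measures use during it.

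Several other objections stand and limit the point:

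- The general Aim 3 objective speaks only of treatment outcome, and the week-12 regressions do address that. A reader might infer that Aim 3 goes untested. It does not; only 3(a) as worded does.
- A reader might infer that no post-treatment day can enter the test. That holds only for completers assessed at about session 12. A later visit, or early departure from treatment under the intent-to-treat approach with outreach to dropouts, would put some post-treatment time in the window, though not by design.
- The Aim 3 sentence does not repeat the outcome definition, so the unit mismatch rests on carrying over the Aim 2 definition.
- A reader might use the anticipated correlation below .20 between repeated opioid measures to argue that week-12 use cannot stand in for later use. Section VI gives that value for Aim 2, in support of a baseline to end-of-treatment difference. Nothing says that it applies between week 12 and follow-up.
- A reader might also argue that the Aim 3 effect size belongs to a different outcome, because it is justified "based on previous studies examining stress reactivity and alcohol and cocaine use following treatment". Section VI gives no numeric Aim 3 effect, and the units and windows of those studies cannot be checked from the documents.

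**Conclusion.** The point holds in a limited form. Hypothesis 3(a) and its only planned test disagree on the window and, by the only definition given, on the unit. For a completer assessed at about week 12, 0 of the 4 look-back weeks fall after treatment; if the visit is 1-2 weeks late, 1-2 of 4 do. No analysis of days of use is planned.

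This rests on two assumptions: that the Aim 2 outcome definition applies to Aim 3, and that the post-treatment assessment falls close to session 12. The documents do not support the stronger readings that Aim 3 is untested or that post-treatment use is wholly excluded.

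The matter concerns a predictor hypothesis in a Stage 1 trial and does not touch the randomized comparison. It should still be settled before analysis, because it determines what may be claimed about use after therapy.

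**What to change.** In section VI, define the 3(a) opioid outcome as the number or proportion of Timeline Follow-Back days with illicit opioid use from the end of treatment through the 1- and 3-month follow-ups. Use observed days as denominator or offset, and adjust for baseline use and treatment arm. State how the end of treatment is dated for participants who leave early. Keep the week-12 regression as a secondary analysis, labelled as end-of-treatment.

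Set the recall period at the follow-up visits to cover the whole interval. The instrument is already scheduled there, but neither section V.4.1 nor Table 1 states how far back it reaches at those visits. Four-week look-backs at about weeks 16 and 24 would cover weeks 13-16 and 21-24 and leave weeks 17-20 unobserved.

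If the sponsor intends the week-12 endpoint, reword 3(a) to match its unit and window, and do not report the result as use following treatment. This also removes the inconsistency but gives up the post-treatment question.

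The first option costs SAP wording, one derived variable, a stated recall period and some follow-up loss: the detectable partial r for one predictor rises from about 0.36 to 0.38-0.40 with 10-20% loss. No new visit or instrument is needed.
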